9.1.1. Incidence of Adverse Events

Summaries of the total number of TEAEs and the number and percentage of subjects with at least 1 TEAE will be provided by actual treatment group and ordered by SOC and PT. This summary will be repeated for pre-study treatment (i.e. AEs starting before the exposed period as defined in [Section 9.1](#)) and post-study treatment AEs (i.e. AEs starting after the exposed period as defined in [Section 9.1](#)).

Treatment-emergent AEs will be presented in descending order from the SOC with the highest total incidence (that is, summed across all treatment groups) to the SOC with the lowest total incidence. If the total incidence for any 2 or more SOCs is equal, the SOCs will be presented in alphabetical order. Within each SOC, the PTs will be presented in alphabetical order. At each level of subject summarization, a subject is counted once if the subject reported 1 or more events.

Common AEs are defined as those reported by more than 5% of the subjects in any of the treatment arm. Summaries of common AEs and common non-serious AEs will be provided (no rounding for the percentage will be used in terms of 5% threshold, e.g. event with 4.9% incidence rate should not be included in this table). The summary will be displayed in descending order of incidence in total column by PT only.

The proportions of subjects with common AEs and relative risks will be summarized for the six comparisons. This will be done using the RELRISK option of the table statement of the SAS PROC FREQ procedure.

Incidences per 100 subject-year will be calculated for the 3 groups of AEs described below, for each SOC and PT. The table will include the number of subjects and AEs, the total subject-years of exposure, the incidence per 100 subject-years of exposure as well as the 95%CI (exact Poisson confidence intervals). For each subject, the duration of exposure is defined as follows:

- For subjects who have an event: from 1st dose of SC IP until the occurrence of the first event.
- For subjects who do not have an event: duration of exposed period.

The exposure-adjusted incidence rates will be calculated for 3 groups of AEs:

- All AESIs (for each category, SOC and PT)
- All fatal serious AEs (for each SOC and PT)
- All SAEs (for each SOC and PT)

All AEs will be listed and TEAEs, pre-study treatment and post-study treatment AEs will be flagged. Additionally, a listing of subject identification numbers for each individual AE preferred terms will be produced.

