4.6.4. Missing Data Handling Rules

For cases where the baseline data is missing, no imputations will be performed.

GCA formal/suspected diagnosis Imputation Dates:

Time since formal diagnosis is defined as: Randomization date - formal diagnosis date + 1

Time since suspected diagnosis is defined as: Randomization date - suspected diagnosis date + 1

Partial dates for suspected/formal diagnosis recorded in the eCRF will be imputed using the following:

- If the day of suspected diagnosis is missing then day will be set to “01” month.
- If the month of suspected diagnosis is missing then month will be set to “January”.
- If either the day or month is missing for formal diagnosis then the following rules will be applied:

- If the day of formal diagnosis is missing then it will be set to “01” or to the day of suspected diagnosis, only if the year and month of suspected and formal diagnoses are equal – whichever is later.
- If the month of formal diagnosis is missing then it will be set to “January” or to the month of suspected diagnosis, only if the year of suspected and formal diagnoses are equal – whichever is later.

Concomitant Medication and Adverse Events Imputation Dates:

The following method will be used to impute missing dates for concomitant medications and adverse events (AE):

Missing start dates (where UK and UKN indicate unknown or missing day and month, respectively):

- UK-*MMM*-*YYYY*:
 - If the month and year are different from the month and year of first SC IP dose in Part A, assume 01-*MMM*-*YYYY*.
 - If the month and year are the same as the first study dose month and year and the stop/end date (after any imputation) is on or after first SC IP dose in Part A, then assume the date of first SC IP dose in Part A.
 - If the month and year are the same as first SC IP dose in Part A month and year and the stop/end date (after any imputation) is prior to first SC IP dose in Part A, then assume the stop/end date for the start date.
- DD-UKN-*YYYY*/UK-UKN-*YYYY*:
 - If the year is different from the year of first SC IP dose in Part A, assume 01-JAN-*YYYY* of the collected year.
 - If the year is the same as first SC IP dose in Part A year and the end date (after any imputation) is on or after first SC IP dose in Part A, then assume the date of first SC IP dose in Part A.

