9.1. Adverse Events

The definition of an AE is detailed in Section 12.4.1 in Appendix 4 of the protocol.

Treatment-emergent AEs:

A treatment-emergent AE for Part A is defined as an AE with a start date during the exposed period.

The exposed period is defined as the period from the 1st dose of SC IP to:

- Early withdrawal: last dose of SC IP + 16 weeks

- Completers (subjects who attended the week 52 visit):
 - Week 52 visit if entering into part B
 - Last dose of SC IP + 16 weeks if not entering into part B

Unless otherwise specified, AE outputs will be based on TEAEs.

All AEs will be coded by system organ class (SOC) and preferred term (PT) according to the Medical Dictionary for Regulatory Activities (MedDRA, Version 19.0 or higher).

An overview summary of TEAEs, including counts and percentages of subjects will be generated by actual treatment group, with any of the following categories:

- Any TEAE, TEAEs related to study treatment (SC IP and/or prednisone study drug), TEAEs leading to permanent discontinuation of study treatment, TEAEs leading to dose interruption/delay, TEAEs leading to dose reduction, TEAEs leading to dose increase, TEAEs leading to dose not changed.
- Any serious TEAEs, serious TEAEs related to study treatment (SC IP and/or prednisone study drug), fatal serious TEAEs, and fatal serious TEAEs related to study treatment.
- Any TEAE of special interest (TEAESI) (see [section 9.1.8](#) for further details), TEAESIs related to study treatments (SC IP and/or prednisone study drug), TEAESIs leading to permanent discontinuation of study treatment, TEAESIs leading to dose reduction, TEAESIs leading to dose increase, TEAESIs leading to dose not changed, TEAESIs leading to dose interruption/delay.

A listing presenting the relationship between SOC, PT, and AE reported will be provided.

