11.4.2. Endpoints from Part A Reported during Part B

The following efficacy endpoints will be summarized and listed for Part B as for Part A using the by-line as specified in [Section 11](#), unless otherwise specified. The visit displayed in the outputs will be the re-mapped visit as specified in [Section 11.5](#).

- Cumulative prednisone dose over time:
Derivation will be the same as for Part A, as described in [Section 8.2.1](#). Only corticosteroid rescue therapies, as defined in [Section 3.3](#) and [Section 7.3](#) will be taken into account in the derivation of cumulative prednisone dose over time. All medication taken the day after the Week 52 visit of Part A will be considered in the analysis.
An additional summary will be displayed taking into account prednisone dose taken during both Part A and Part B.
- Number of disease flares per subject over time:

Derivation will be the same as for Part A, as described in [Section 8.2.4](#). All events occurring the day after the Week 52 visit of Part A will be considered in the analysis. The summary table will not use the Part B by-line.

An additional summary will be displayed taking into account all flares occurring during both Part A and Part B.

- Proportion of subjects requiring hospitalizations for disease flare and number of hospitalizations for disease flare over time:
Derivation will be the same as for Part A, as described in [Section 8.2.5](#). All events occurring the day after the Week 52 visit of Part A will be considered in the analysis. The summary table will not use the Part B by-line
- Patient-reported outcomes including SF-36v2 acute, EQ-5D (5L), FACIT-Fatigue, Pain NRS, Steroid Impact Questionnaire, HAQ-DI, PtGA and PhGA are exploratory endpoints in Part B and will only be listed

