11.5. Adverse Events

Since some subjects may not take any study drug during Part B, all AEs (not only TEAEs) will be summarized for Part B. An AE for Part B is defined as an AE starting from the Part A Week 52 visit date or the first SC IP of the Part B open-label treatment, whichever is earlier, to the end of study.

All adverse events summary table will be duplicated:

- The first table will use the byline: “Never Received OL Sirukumab during Part B” vs. “Received at Least 1 Dose of OL Sirukumab during Part B”
- The second table will use the following byline:
 - “Exposed” adverse events: Defined as all AEs occurring within 16 weeks after Sirukumab (SC IP or OL Sirukumab intake during Part B)
 - “Non-exposed” adverse events: Defined as all AEs not occurring within 16 weeks after Sirukumab (SC IP or OL Sirukumab intake during Part B)

It is important to note that all adverse events occurring during Part B within 16 weeks after the last intake of SC IP will be considered as “Exposed”, even if a subject never took OL Sirukumab during Part B.

No adverse events leading to discontinuation of study that is related to prednisone study drug will be displayed since prednisone study drug is only taken during Part A. TEAE related to prednisone will be displayed for Part B (instead of related to prednisone study drug for Part A).

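### The Part A 'post-study treatment' AE category has no cut-off at Part B entry, and two boundary rules at Week 52 and open-label start can also misfile events

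*SAP*

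**What the plan says.** - **Exposed period (SAP 9.1).** It runs from the first SC dose. For a completer it ends at the "Week 52 visit if entering into part B", or otherwise at "Last dose of SC IP + 16 weeks if not entering into part B".
- **Post-study category (SAP 9.1.1).** The TEAE summary, which "will be provided by actual treatment group and ordered by SOC and PT", is repeated for "post-study treatment AEs (i.e. AEs starting after the exposed period as defined in" Section 9.1. The listing of all AEs carries the matching flag. No upper date is stated.
- **Part B AEs (SAP 11.5).** "An AE for Part B is defined as an AE starting from the Part A Week 52 visit date", or from the first open-label dose if that is earlier, up to the end of the study. Part B tables are split by receipt of open-label drug and again by exposure: "all adverse events occurring during Part B within 16 weeks after the last intake of SC IP will be considered as" 'Exposed'.
- **Boundary for other Part B endpoints (SAP 11.4.2).** For flares and hospitalizations the count begins one day later: "All events occurring the day after the Week 52 visit of Part A will be considered in the analysis". Cumulative prednisone uses the same boundary.
- **Partial AE start dates (SAP 4.6.4).** With only the day unknown: "If the month and year are different from the month and year of first SC IP dose in Part A, assume" the first of that month. With the month unknown and a year other than that of the first Part A dose, 1 January is used. The first open-label dose does not enter these rules.

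**The concern.** The post-study category is meant for events after treatment has ended. For a Part B entrant it opens the day after the Week 52 visit, when the subject may be starting open-label sirukumab 100 mg q2w (available whatever the Part A arm) or may still be inside the 16-week window that the SAP treats as exposure elsewhere. An on-sirukumab event in a former Arm D or E subject would then sit in a placebo column under an off-treatment label, and appear again in Part B, possibly as 'Exposed'. The table would also mix two populations: non-entrants counted from 16 weeks after the last dose, and entrants counted from Week 52.

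The two boundary rules matter for a different reason. They decide which part owns an event, so they can alter the Part A TEAE tables themselves. Efficacy is now summarized without statistical analysis (SAP 1.1), so safety tabulations carry most of what the study will report.

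**Working it through.** The plan has no figure of its own to reproduce here. The check applies the date rules of SAP 9.1, 9.1.1 and 11.5 to a Part B entrant.

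**Assumed nominal days.** First SC dose = day 1. Last blinded dose at Week 50 = 50 × 7 + 1 = day 351. Week 52 visit = 52 × 7 + 1 = day 365. Week 50 is taken as the last blinded dose because the protocol's Part A Time and Events table dispenses product at Week 52 only to subjects starting open-label drug. Sixteen weeks = 112 days. Open-label start was tried as none, day 365, and day 533 (365 + 168, Week 24 of Part B).

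| AE start | SAP 9.1 / 9.1.1 | SAP 11.5 |
|---|---|---|
| day 200 | Part A TEAE | not a Part B AE |
| day 365 | Part A TEAE | Part B AE |
| day 366 | post-study treatment | Part B AE; 366 − 351 = 15 days after last SC dose, 'Exposed' |
| day 400 | post-study treatment | Part B AE; 400 − 351 = 49 days, 'Exposed' |
| day 543 | post-study treatment | Part B AE; if open-label began on day 533, 10 days after its first dose, 'Exposed' |
| days 729, 1093 | post-study treatment | Part B AE |

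The 9.1.1 class was the same for every open-label start tried. For a subject who does not enter Part B, the category opens only after day 351 + 112 = 463. The two groups in the same table therefore start 463 − 365 = 98 days (14 weeks) apart.

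**Week 52 date.** Day 365 is inside the Part A exposed period, which ends at that visit, and is also the first Part B day. The event is therefore counted as a Part A TEAE and as a Part B AE, and does not reach the post-study table.

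**Partial dates (hypothetical calendar).** First dose 15 March 2016; Week 52 visit 364 days later, 14 March 2017; open-label drug started at that visit.
- AE recorded as March 2017, day unknown: the month and year differ from March 2016, so it is imputed to 1 March 2017, 13 days before open-label start. It becomes a Part A TEAE.
- AE recorded as 2017 only: imputed to 1 January 2017, 31 + 28 + 13 = 72 days before open-label start. It becomes a Part A TEAE.

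If open-label drug instead starts 168 days later, on 29 August 2017, an AE recorded as August 2017 goes to 1 August. That is before the drug but after Week 52, so it stays in Part B. An AE recorded as 2017 only still goes to 1 January and becomes a Part A TEAE. The unknown-day rule thus crosses into Part A only when the Week 52 visit falls on or after the first of the recorded month. The unknown-month rule crosses when that visit falls on or after 1 January of the recorded year.

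**The case against.** The best answer is that SAP Section 1 says Sections 4 to 10 focus on Part A, while Section 11 gives Part B its own AE definition and reproduces all safety summaries. The authors probably meant Part B events to be left out of 9.1.1. That is fair as to intent, and a reader should not infer a deliberate plan to pool Part B events with Part A. It does not settle the programming, because a scope sentence is not a data cut. Where a cut was wanted one was written: SAP 7.1 ends Part A concomitant medications at the Week 52 visit or the first open-label dose, whichever is earlier.

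Second, a reader might infer that the main safety comparison is misstated. The documents do not support that. SAP 9.1 bases AE outputs on TEAEs by default, and for Part B entrants TEAEs stop at the Week 52 visit. The TEAE incidence, severity, relatedness and relative-risk outputs are therefore untouched by the open-ended category. SAP 11.5 also already separates Part B events by open-label receipt and by exposure. Using Part A arms as columns is the stated layout for Part B too (SAP 11), so it is not an error in itself. This part of the objection stands.

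Third, the Week 52 overlap mirrors the concomitant-medication rules (7.1 and 11.3), and including that date in Part B makes sense for someone who starts open-label drug at the visit. That explains the choice but does not remove the double count. The partial-date problem needs an incomplete AE date, and nothing shows how often one occurs. That limits its size, not its validity.

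**Conclusion.** The point holds as a missing bound with a real internal conflict. As written, any AE starting after the Week 52 visit date in a Part B entrant is post-study treatment in one place and a Part B AE, possibly 'Exposed', in another. Events on the Week 52 date itself are excepted, so it would be wrong to say that every Part B event is swept in. The reach is one descriptive Part A table and the listing flag.

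The boundary rules are narrower in count but reach further. The Week 52 date is double counted, and an incomplete date can turn an on-open-label event into a Part A TEAE under the original arm, placebo included.

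No size can be given. The documents do not state how many subjects entered Part B, how many started open-label drug, or how many AE dates are partial. Protocol dates and the planned 3:3:2:2:2 allocation cannot stand in for these: the study stopped early, and SAP 1.1 reports only a limited number of Week 52 completers. The conclusion rests on a literal reading of 9.1, 9.1.1, 11.5 and 4.6.4. The day numbers and calendar dates above are illustrative.

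**What to change.** 1. **SAP 9.1.1.** Limit Part A post-study treatment AEs, and the listing flag, to subjects who do not enter Part B, with onset after the last SC dose plus 16 weeks. For entrants, events after Week 52 are then reported only under 11.5.
2. **SAP 9.1 and 11.5.** Assign an AE on the Week 52 visit date to one part: Part B if open-label drug is started that day, otherwise Part A.
3. **SAP 4.6.4.** For subjects who took open-label drug, impute an AE start to the first open-label dose date when the partial date is compatible with that date and the AE does not end before it. Apply this before the first-of-month and 1 January defaults. With item 2, such an event falls in Part B even when open-label drug began at the Week 52 visit.

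The cost is about three SAP sentences, one table and its flag to reprogram, and one addition to the AE date-imputation code. No new data are needed. It should be done before database lock.

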9.1.2. Relationship of Adverse Events to Study Treatments

A separate summary will be provided for study treatment-related TEAEs. A study treatment-related TEAE is defined as a TEAE for which the investigator classifies the relationship to study treatment (subcutaneous IP or prednisone study drug) as “Yes”. One summary table will be produced. The table will be split in five parts: TEAEs Related to SC IP (regardless of relationship to Prednisone), TEAEs related to both SC IP and prednisone study drug, TEAEs related to SC IP only, TEAEs related to prednisone study drug (regardless of relationship to SC IP), TEAEs related to prednisone study drug only. A worst-case scenario approach will be taken to handle missing relatedness data (i.e. TEAEs with missing relationship will be considered as TEAEs related to study drug). The summary table will be displayed in descending order of incidence in the total column by SOC and PT. A separate table will also display the summary by severity (as for all AEs).

9.1.3. Severity of Adverse Events

A summary of TEAEs by severity (SOC and PT) will be presented in a table. The severity that will be presented represents the most extreme severity captured on the eCRF page. The possible severities are “Mild,” “Moderate,” and “Severe.” In the TEAE severity table, if a subject reported multiple occurrences of the same TEAE, only the most severe will be presented. Treatment-emergent AEs that are missing severity will be presented in tables as “Unknown” and will be presented in the data listing with a missing severity.

9.1.4. Serious Adverse Events

The definition of a SAE is detailed in Section 12.4.2 in Appendix 4 of the protocol.

All serious TEAEs will be tabulated based on the number and percentage of subjects who experienced the event. Separate summaries will also be provided for:

- Study treatment-related serious TEAEs,
- Fatal serious TEAEs,

- Treatment-related fatal serious TEAEs.

The summary tables will be displayed in descending order of incidence in total column by SOC and PT, or PT only depending on the output.

All SAEs are included in the listing of all adverse events. Separate supportive listings with subject-level details will be generated for all SAEs (including details of why AE was considered as serious based on reasons given on the SAE page).

9.1.5. Adverse Events Leading to Permanent Discontinuation of Study Treatments

Treatment-Emergent AEs leading to discontinuation of study treatment (subcutaneous IP or prednisone study drug) will be summarized. One summary table will be produced. The table will be split in two parts: one part for TEAEs leading to permanent discontinuation of SC IP and one for TEAEs leading to permanent discontinuation of prednisone study drug. All subjects who have an AE where the outcome is marked as “Study Treatment(s) withdrawn” is “Yes” will be summarized in a table by SOC and PT. All data will be listed.

9.1.6. Adverse Events Leading to Dose Interruption / Delay of Study Treatments

Treatment-Emergent AEs leading to dose interruption / delay of SC IP will be summarized. One summary table will be produced. The table will summarize TEAEs leading to dose interruption / delay in SC IP. All subjects who have an AE where the action taken with SC IP is marked as “Dose interrupted / delayed” will be summarized in a table by SOC and PT. All data will be listed. TEAEs leading to dose interruption / delay in SC IP and/or dose interruption / delay in prednisone study drug will be listed.

9.1.7. Death

Fatal SAEs will be listed. Listings of death certificate details and cause of death will be generated to provide subject-specific details on subjects who died prior to study completion.

9.1.8. Adverse Events of Special Interest

The identification, classification and adjudication of adverse events of special interest (AESI) will occur in a blinded fashion quarterly by the GSK medical monitor. The final adjudication will take place prior to database releases and will be performed for reporting purposes.

Where available, AEs will have SMQ flags assigned to help the adjudication process at GSK. These flags will help but not over-rule individual event adjudication performed by GSK. All AE terms will be adjudicated at the subject level by GSK, in order to identify any events that are AESI as defined by the protocol as well as to assign each AESI category which will support later tabulation.

The groups of adverse events of special interest are defined below:

- Gastrointestinal perforation
- Diverticulitis
- Tuberculosis activation
- Serious/opportunistic infections

- Hypersensitivity
- Cytopenias
- Serious cardiovascular events
 - Major Adverse Cardiac Events (MACE) adjudicated by the CEC
 - MACE
- Malignancies
- Injection site reactions
- Severe flares including hospitalizations
 - Total/partial blindness
 - Limb claudication
 - Scalp or tongue necrosis
- Lipid increases
- Liver function test abnormalities
- Corticosteroid-related AE

An overall summary of AESIs will be presented summarizing numbers and percentages of subjects with events within each of the above categories as well as by SOC and PT.

Further details will be provided in summaries of each AESI separately. The summary of event characteristics will also be provided, including number of subjects with at least one event, number of events, the event characteristics (i.e. seriousness, relationship to study drug, severity and if the event was fatal or not), the number of occurrences, the outcome, the maximum intensity and the action taken. The worst case approach will be applied at subject level for the event outcome and the action taken, (i.e. a subject will only be counted once as the worst case from all of the events that that subject had). In addition, onset and duration of the first occurrences for each type of events will be summarized.

Time to onset of first AESI will be displayed and calculated as:

$$\text{Date of onset of first AESI} - \text{Date of first SC IP date} + 1 \text{ day}$$

Duration of first AESI will be displayed and calculated as:

$$\text{End date of first AESI} - \text{Start date of first AESI} + 1 \text{ day}$$

The proportions of subjects with AESIs and relative risks for the six comparisons will be summarized in a table. This will be done using the RELRISK option of the table statement of the SAS PROC FREQ procedure.

A supportive listing of all AESI will be presented.

